1.0 Study Summary

Study Title	An investigation of a parent/child psycho-social	
	computerized intervention targeting the error-related	
	negativity in young children	
Study Design	This is a 5-year training grant wherein during the 1st year of	
	the award, PI, [name], will develop a novel	
	computerized intervention for parents and children that aims	
	to reduce over-reactivity to making mistakes.	
Primary Objective	Reduce over-reactivity to making mistakes in children.	
Secondary		
Objective(s)		
Research	A novel computerized intervention for parents and children	
Intervention(s)	that aims to reduce over-reactivity to making mistakes.	
Study Population	175 parent/child dyads with children between the ages of 5	
	and 7 years-old	
Sample Size	175 parent/child dyads	
Study Duration for	6 months	
individual		
participants		
Study Specific	ERN = error-related negativity	
Abbreviations/		
Definitions		

2.0 Objectives*

2.1 AIM 1: Assess initial target engagement by examining whether a neural marker of risk for anxiety (i.e., the ERN) in children is decreased during a single lab visit, via a brief, computerized intervention designed to target error sensitivity. We hypothesize that children who receive the intervention will display a decrease in the ERN at the first assessment, compared to children in the control condition. 1a. Assess alternate measures of target engagement. Self-report and observational measures of error sensitivity will also be decreased for parents and children who receive parent and child active interventions, respectively. AIM 2: Examine whether children in the intervention conditions display a reduction in the ERN from the initial lab assessment to the six-month follow-up assessment. We expect that children in all treatment conditions (parent/child, parent only, child only) will display a reduced ERN compared to the control group. 2a. Dissociate the impact of parent/child, parent only, versus child only treatment conditions. We hypothesize that children in the combined treatment group (parent/child) will have the greatest reduction in the ERN. 2b. Examine the impact of utilization. We expect that parents and children who utilize the treatment materials more frequently will experience the greatest reduction in the ERN. 2c. Assess alternate measures of target engagement. We will also examine all hypotheses in relation to self-report and observed measures of parent and child error sensitivity. AIM 3: Examine whether parent/child dyads in the intervention conditions experience changes in anxiety symptoms at the six-month follow-up. We hypothesize that the dyads in the intervention conditions will experience greater changes in anxiety symptoms compared to the control group. We will also compare conditions, as well as examine the impact of utilization. In exploratory analyses, we will examine to what extent changes in the ERN and error-sensitivity relate to changes in anxiety symptoms in children.

3.0 Background*

3.1 Anxiety disorders are the most common form of psychopathology, and are associated with substantial impairment. Longitudinal-prospective work demonstrates that anxiety disorders often begin in childhood and persist across the lifespan. Therefore, there is a critical need and opportunity to identify markers of risk that predict anxious trajectories of development. Markers that are evident before symptoms become impairing may be novel targets for intervention. One promising biomarker of anxiety is increased brain activity in response to errors, as reflected by the error-related negativity (ERN). The ERN is a deflection in the eventrelated potential (ERP) occurring after an individual makes a mistake on

lab-based tasks. In over 45 studies to date, the ERN has been found to be increased in anxious individuals, including children as young as age. Critically, an increased ERN has also been shown to predict the onset of new anxiety disorders in children and adolescents, even while controlling for baseline anxiety symptoms and other known risk factors.

Considering the ERN is elevated before anxiety symptoms become impairing, it is crucial to identify factors that may modify the ERN early in life – and determine if doing so can prevent the onset of clinical anxiety. Given that the ERN can be potentiated in the lab by punishment for errors8, we hypothesized that exposure to critical parenting styles may sensitize children to their own mistakes. Indeed, we found that both observational and self-report measures of critical parenting style related to an increased ERN in offspring in a large sample of young children. This finding has since been replicated in even younger children (approximately 4 years old), suggesting that the ERN is a neural risk marker for anxiety that can be shaped by parenting behaviors. This raises the possibility that the ERN might also be modified by targeting specific parenting behaviors, and thus, may be a modifiable biomarker. However, no previous work has examined whether modifying parenting can impact the ERN. Moreover, no previous work has examined the extent to which any targeted intervention may impact the ERN in children.

3.2 In my lab, we have recently collected pilot data suggesting that the ERN can be reduced in children undergoing a brief, computerized, psychosocial intervention targeting reactivity to making mistakes. Drawing upon this and other work, in the current proposal, we will develop a novel psychosocial intervention that targets over-reactivity to children's errors, which can be administered to parents and children, or both, which aims to reduce the ERN in children.

3.3 The proposed Mentored Career Development Award (K01) is designed to extend my previous work on the ERN, parenting, and risk for anxiety in young children to test the extent to which the ERN can be modulated. Specifically, we will recruit 175 parent/child dyads, high in error sensitivity, and randomize them to a parent/child treatment condition, parent only treatment condition, child only treatment condition, or control condition. We will measure the ERN in children pre and post intervention. Parents and children in active conditions will have access to additional online materials between the baseline and follow-up visit. At a six-month follow-up, we will again assess children's ERN, error sensitivity, and anxiety symptoms. My training plan builds on my expertise on the ERN and anxiety, and integrates training in the design and implementation of computerized interventions, as well as advanced statistical analyses related to intervention outcomes.

4.0 Study Endpoints*

4.1 Participants will come into the lab for a baseline visit and return to the lab 6 months later for a follow-up visit.

5.0 Study Intervention

Description: As part of the current proposal, during Year 1, we 1.1 plan to develop a computerized intervention to be administered to parents and children separately. All participants in an active condition (parent/child, parent only, or child only) will receive the initial treatment session in the baseline lab visit. Additional materials that expand upon the concepts presented in the 1st session will be available online for children and parents between the baseline and follow-up assessment (depending on condition, e.g., in parent only condition, only parents will have access to between-session materials). These materials will include worksheets, games, and handouts. Participants will be told that participation in these additional online modules is optional and we will send a weekly reminder (via email or text) to remind them of concepts from the initial session, as well as provide the links to the additional materials. We will track utilization of the additional materials in parents and children. Additionally, as part of these additional modules, we will periodically ask parents and children to complete the Error Sensitivity Index to track changes across the 6 months between lab assessments. The development of this intervention, and testing its impact on ERN, is the primary goal of the proposed training grant. [name] is an expert in the area of computerized treatments for anxiety and will aid in the development and implementation of the intervention. Additionally, Drs. [name], [name], [name], and [name] all have expertise in intervention development and I will consult with them regularly during the development phase of the training grant. For the child intervention, we will use developmentally appropriate language, as well as stories that children between the ages of 5 and 7 can understand and relate to. We will train research assistants to guide children through the computer intervention and answer questions when children appear to be confused. We used this approach successfully when administering the Child Error Sensitivity Index to children between the ages of 5 and 7 years-old, as well as during pilot data collection. This intervention will be based on the constructs in the Child Error Sensitivity Index, as well as other constructs, that relate to the ERN – for example, perfectionism, fear of evaluation from others, and over-valuation of the negative consequences of errors. The intervention will focus on basic concepts such as: "making mistakes is how we learn new things", "everybody makes mistakes", and "good things come from mistakes." While the first session will focus primarily on constructs in the Child Error Sensitivity Index, the additional online materials will expand beyond this. For example, we will cover other constructs that may also relate to the ERN: e.g., tolerance of uncertainty, distress tolerance, mindfulness, constructive self-talk, facing fears, identifying sensations of anxiety, avoidance, behavioral inhibition, checking behavior, etc. - all in the context of, or relating to, performance monitoring or error sensitivity. The intervention will be

interactive, including games and recorded vignettes, as well as questions to gage children's comprehension of the concepts being presented. To collect pilot data, we created a very preliminary version of this computerized intervention to collect pilot data in young children. This preliminary intervention can be viewed at: https://www.youtube.com/watch?v=1wUNqdQ91Io&t=10s.

The parent version of the intervention will include these same basic concepts, but will also target parenting style and provide psychoeducation on the negative impact of over-reacting to children's mistakes. The parent version will also include examples of how to model appropriate reactivity to mistakes, and provide video vignettes and examples of both critical and adaptive parenting reactions to mistakes. The parent intervention will also provide feedback to the parent on how reactive they tend to be to their children's errors and provide a structured way for parents to plan to reduce their reactivity to their children's mistakes. For example, planning positive reinforcement strategies and how to avoid criticality in specific situations. We will also explore various motivations that parents may have for hyper-reactivity to children's errors (for example, the motivation to punish errors vs. preventing the child from failing and experiencing negative emotions) and discuss ways to increase awareness of these motivations, as well as the negative consequences of this behavior on children. Additionally, we will offer replacement behaviors, as well as examples of how to integrate these new behaviors into daily activities. Both interventions will be designed to last approximately 45 minutes. The format of the interventions will be based on [name] previous work using brief-computerized interventions. We will also consult with Drs. [name], [name], and [name], who all have expertise in the design of parenting interventions. Additionally, as stated above, we will provide parents in the active condition with weekly reminders and additional online materials. We have created a preliminary version of this computerized intervention for our pilot sample. This preliminary intervention can be viewed at:

```
https://www.youtube.com/watch?v=3qN0Hco17VI.
```

For the control condition, we plan to utilize an active control previously used by [name]. This will be a computerized presentation, in the same format as the active intervention, but will focus on self-care topics – unrelated to error sensitivity. The computerized control presentation will be administered to both parents and children. Participants in the control condition will have access to online materials related to self-care between assessments. We view the current proposal as a first step in the development of a novel intervention targeting error sensitivity. If we are able to demonstrate initial target engagement (i.e., reduce the ERN), in future studies, we plan to examine the potential impact of dose and whether this intervention can provide incremental symptom reduction, in addition to existing treatment approaches for child anxiety.

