Additionally, to assess error sensitivity in children, we will use our previously validated measure (i.e., the Child Error Sensitivity Index), before and after the intervention, and at follow-up. This measure includes 9 items indexing error sensitivity, for example: "I feel upset when other people don't like something I have done", "If I make a mistake, I always want to fix it", and "When I make a mistake, I feel anxious", and has good psychometric properties.

We will also assess parent's sensitivity to their child's errors before and after the intervention, and at follow-up. Our measure of Parent Sensitivity to Children's Errors includes 20 items, such as the following: "When I notice a mistake my child made, I feel upset", "If my child makes a mistake, I have a strong urge to fix it immediately", "When my child makes a mistake, I feel anxious", "I like to watch my child do things to make sure she/he doesn't make mistakes."

Additional self-report measures include the following (all will be uploaded under documents section):

Child:

Child and Adolescent Perfectionism Scale CRPBI CASI Child report: parent sensitivity to my errors Acceptability Measure

Parent:

IDAS Parent ASI to child Parent ASI FASA Parent report on child's error sensitivity Parent sensitivity to child's errors Parent error sensitivity Avoidance questionnaire CBQ PSDQ CRPBI Acceptability Measure Child Anxiety Life Interference Scale – Preschool Version (CALIS-PV) Coping with Children's Negative Emotions Scale (CCNES) Spence Preschool Anxiety Scale (Parent Report)

Observational behavioral task. We will also use a lab-based observational task to measure error sensitivity in children, as well as parent's sensitivity to their children's errors, before and after the intervention, and at the follow-up lab visit. These will be tasks that we have utilized in a previous study at FSU in this same age-range.

Episode 1: Guessing Card Game (Headbands).

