17.0 Data Management* and Confidentiality

Data analysis plan: AIM 1: Assess initial target engagement by 17.1 examining whether a neural marker of risk for anxiety (i.e., the ERN) in children is decreased during a single lab visit, via a brief, computerized intervention designed to target error sensitivity. We hypothesize that children who receive the intervention will display a decrease in the ERN at the first assessment, compared to children in the control condition. 1a. Assess alternate measures of target engagement. Self-report and observational measures of error sensitivity will also be decreased for parents and children who receive parent and child active interventions, respectively. AIM 2: Examine whether children in the intervention conditions display a reduction in the ERN from the initial lab assessment to the six-month follow-up assessment. We expect that children in all treatment conditions (parent/child, parent only, child only) will display a reduced ERN compared to the control group. 2a. Dissociate the impact of parent/child, parent only, versus child only treatment conditions. We hypothesize that children in the combined treatment group (parent/child) will have the greatest reduction in the ERN. 2b. Examine the impact of

utilization. We expect that parents and children who utilize the treatment materials more frequently will experience the greatest reduction in the ERN. 2c. Assess alternate measures of target engagement. We will also examine all hypotheses in relation to self-report and observed measures of parent and child error sensitivity. AIM 3: Examine whether parent/child dyads in the intervention conditions experience changes in anxiety symptoms at the six-month follow-up. We hypothesize that the dyads in the intervention conditions will experience greater changes in anxiety symptoms compared to the control group. We will also compare conditions, as well as examine the impact of utilization. In exploratory analyses, we will examine to what extent changes in the ERN and errorsensitivity relate to changes in anxiety symptoms in children.

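### Aim 1a re-asks the error-sensitivity scales soon after a session built on those constructs, so a same-day fall against control is not independent evidence of target engagement

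*Combined protocol and SAP*

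**What the plan says.** Section 5.0 takes the content of the child session from the outcome scale: "This intervention will be based on the constructs in the Child Error Sensitivity Index", and "the first session will focus primarily on constructs in the Child Error Sensitivity Index". The session also contains "questions to gage children's comprehension of the concepts being presented". The parent session carries the same core messages, explains that over-reacting does harm, and has the parent plan to react less. It also includes personal feedback: "The parent intervention will also provide feedback to the parent on how reactive they tend to be".

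Section 6.3 schedules the 9-item child scale ("i.e., the Child Error Sensitivity Index), before and after the intervention, and at follow-up") and gives the 20-item parent scale the same three time points ("errors before and after the intervention, and at follow-up. Our measure of Parent Sensitivity"). The first two fall within one visit of about 2 to 3 hours.

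Section 5.0 gives control families a presentation in matching format on self-care, with no content on errors.

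Sections 2.1 and 17.1 both carry the heading "1a. Assess alternate measures of target engagement" and predict: "Self-report and observational measures of error sensitivity will also be decreased for parents and children who receive parent and child active interventions, respectively".

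**The concern.** In the treated arms, the person who answers the post-session scale has just been taught how mistakes should be viewed, in material drawn from that scale's constructs. Parents have also been told how reactive they are and asked to plan a change. Control participants have had none of this. The control therefore matches attention and format, but not exposure to the desired direction of answer.

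A same-day difference between arms on these scales could reflect lower error sensitivity, knowledge of the expected answer, or both, and the comparison cannot separate them. The plan does not require a fall on self-report to be matched by the ERN or by observed behaviour. It specifies no measure of demand or social desirability, and describes no blinding of participants, research assistants or video coders. At stake is whether visit-1 self-report may be cited as separate corroboration that the intervention reached its target.

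**Working it through.** The plan gives no test, alpha, SD or expected effect for Aim 1a, so there is no figure to reproduce. The check has two parts: the sequence of events, and an illustration under stated assumptions.

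**Sequence**

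1. Source of content: the child session comes mainly from the index constructs; the parent session adds parenting style and personal feedback (5.0).
2. Outcome: the same child index and the parent index (6.3).
3. Order for the child: session, then EEG task, observational task and questions (6.3, procedure paragraph).
4. Order for the parent: the procedure paragraph mentions questionnaires and session together without ordering them. That feedback precedes the second parent score follows from the before-and-after schedule given with the measure in 6.3.
5. Comparator: self-care content (5.0). Aim 1a names no comparator; control is carried over from Aim 1.
6. Claim: a fall counts as an alternate measure of target engagement (2.1, 17.1).

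**Illustration**

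Inputs from 6.1: 50 parent/child + 50 child only = 100 children given the child session; 50 parent/child + 50 parent only = 100 parents given the parent session; 25 control dyads.

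Assumptions not in the documents: no true change, a pure reporting shift d of 0.3 or 0.5 SD in the treated, SD = 1, two-sided alpha 0.05, a normal approximation, complete visit-1 data, and a pre-post correlation r of 0.5 or 0.7 where baseline is adjusted for.

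- Unadjusted SE = sqrt(1/100 + 1/25) = sqrt(0.05) = 0.224 SD. The smallest significant shift is 1.96 × 0.224 = 0.44 SD.
- Adjusted SE = sqrt(0.05 × (1 − r²)): sqrt(0.05 × 0.75) = 0.194 at r = 0.5, and sqrt(0.05 × 0.51) = 0.160 at r = 0.7.
- Chance of a significant fall = P(Z > 1.96 − d/SE).

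| Analysis | SE (SD) | d = 0.3 | d = 0.5 |
|---|---|---|---|
| Unadjusted | 0.224 | 27% | 61% |
| Adjusted, r = 0.5 | 0.194 | 34% | 73% |
| Adjusted, r = 0.7 | 0.160 | 47% | 88% |

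With no shift, the chance of a significant fall is 2.5%. For one active arm against control (50 v 25, unadjusted), the smallest significant shift is 0.48 SD and the chances are 23% and 53%.

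The calculation shows what a shift of a given size would do. It does not show that such a shift occurs.

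**The case against.** Four arguments favour the plan.

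- **The overlap is of constructs, not item wording.** The taught messages are general statements about mistakes, while the sample items ask about feelings and urges. Intervening on the construct one measures is ordinary practice. This stands: learned answering is possible but not shown.
- **Little rests on this outcome.** Section 5.0 equates initial target engagement with a reduced ERN and makes later work depend on it. Aim 1a is labelled alternate, its prediction covers self-report and observation jointly, and self-report is repeated at six months. This stands as a limit on the consequence. It does not remove the problem, because no rule makes the self-report result depend on the other measures.
- **The figures assume the bias.** The shift, the correlations and alpha are all assumed. This stands.
- **Observation is no clean substitute.** Section 6.3 codes positive and negative statements about errors at the same visit, soon after participants have heard model statements, and no blinding of coders is described. This stands, and it shapes the fix.

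A reader might infer that Aim 1a is almost certain to succeed on self-report, or that participants would simply recite the items. The documents do not support either reading: the illustrative range is 27% to 88%, it depends on an assumed shift, and no item is shown to be taught.

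**Conclusion.** The concern holds in a limited form. Visit-1 post-session self-report from the taught member follows a session on the same constructs, and the control does not offset this. A same-day fall against control may therefore partly reflect demand or learned answers, and should not stand alone as evidence of target engagement. The size of that part cannot be known from the documents. If it were 0.3 to 0.5 SD, it would yield a significant result in about 27% to 61% of trials unadjusted, or 34% to 88% with baseline adjustment, under the assumptions listed.

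The point concerns how Aim 1a may be interpreted. A reader might extend it to the ERN conclusion, but the ERN is recorded during a task, is less open to learned answers, and is the plan's main target. For parents, the point rests on the order inferred from the before-and-after schedule.

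**What to change.** 1. In both 2.1 and 17.1, which carry the same aim text, describe the taught member's same-visit scores on the two indices as a manipulation check that does not by itself support target engagement.
2. Let the engagement conclusion rest on the ERN, supported by observation coded blind to arm and time point. Count self-report only if one of these agrees or the fall persists at month 6. Persistence is the weaker safeguard, since 5.0 provides weekly reminders of the session's concepts in between.
3. For Aim 2c, keep the same scales in every arm. Giving each arm a different lead informant would break the comparison of active conditions in Aim 2a, and the combined arm has no untaught member.
4. Add the untaught member's report as a supporting analysis: the parent's report on the child's error sensitivity for child only v control, and the child's report of the parent's sensitivity for parent only v control. Section 6.3 lists both scales without time points, so this requires confirming that they are collected at baseline and month 6.

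The cost is wording in two sections, blinded allocation of videos to coders, and the check on time points. No new measure or visit is needed if that check succeeds. The downside is that same-visit self-report no longer counts alone as confirmation.

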6.0 Procedures Involved*

6.1 We plan to recruit 175 parent/child dvads, high in error sensitivity (measured with self-report), and randomize 150 to an intervention condition (50 to parent/child, 50 to parent only, 50 to child only) and 25 to an active control condition. We plan to utilize an unbalanced design (150 intervention versus 25 controls) due to the fact that longitudinal data in developmental samples suggests the ERN is typically stable or increases across development. Therefore, a decrease in the ERN is not expected to occur in the control group. We will measure the ERN in children pre and post intervention, as well as error sensitivity and anxiety symptoms. At a six-month follow-up, we will again assess children's ERN, as well as error sensitivity and anxiety symptoms. We chose a six-month follow-up assessment to allow for adequate time for the parenting intervention to impact children (1-month may be too brief to observe impact), as well as to allow for children and parents to access the additional online materials (24 modules will be offered). This time was also selected to minimize drop-out that might occur over longer follow-up periods.

Further, before and during all in-person lab visits, we plan to take protective measures in order to reduce any possible spread of COVID-19 and to prevent any individuals at higher risk from participating in our study. Provided IRB approval, we plan to resume lab visits on August 1 with these protective measures in place.

6.2 Year 1: intervention development, collect pilot data from 10 parent/child dyads.

Year 2 - 4: recruit and collect data from 6 parent/child dyads per month, total N = 175 parent/child dyads. We will also collect 6-month follow-up data in the lab for each parent/child dyad.

Year 5: complete all follow-ups. Data processing, analysis, statistical procedures and manuscript preparation.

Risks are fairly minimal. There is a chance that some parents or children may experience mild, transient distress during parts of the assessments. All questions (self-report) are the type typically asked during a routine psychological or medical evaluations. If necessary, the assessment can be interrupted or terminated. The family (parent and patient) will be clearly informed that they are free to terminate participation at any point in the protocol.

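### Weekly reminders are specified only for the active conditions, so a six-month active-versus-control difference could not be attributed to error-sensitivity content rather than to prompting

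*Combined protocol and SAP*

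**What the plan says.** All the relevant text is in section 5.0 of the combined protocol and SAP.

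- **Active conditions.** The opening paragraph sets its subject with "All participants in an active condition (parent/child, parent only, or child only) will receive the initial treatment session in the baseline lab visit". It goes on to the optional online materials and says "we will send a weekly reminder (via email or text) to remind them of concepts from the initial session", with links to those materials.
- **Parent version.** The later paragraph on the parent intervention refers back to this and assigns it by condition: "we will provide parents in the active condition with weekly reminders and additional online materials".
- **Control condition.** The session is "in the same format as the active intervention, but will focus on self-care topics", and "The computerized control presentation will be administered to both parents and children". Between visits, "Participants in the control condition will have access to online materials related to self-care between assessments". Reminders are not mentioned here, and no other section gives them to controls.

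On timing, section 4.1 says "Participants will come into the lab for a baseline visit and return to the lab 6 months later for a follow-up visit". Section 2.0 places Aim 1 within the first lab visit and Aims 2 and 3 at the six-month follow-up. Section 6.1 allocates 50 dyads to each of three active arms and 25 to control.

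**The concern.** An active control is there to match everything except the ingredient under test. This one matches the session's format and recipients, and it matches access to online materials. It does not, as written, match prompting. Staff who follow the text would send a weekly message to active families and nothing of the kind to controls.

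That matters for three things measured or accumulated over the six months:

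- **Reported outcomes.** Aim 2c and Aim 3 rest largely on parent and child report of error sensitivity and anxiety (section 6.3). Such measures are open to effects of repeated contact and of expectation.
- **Module use.** The messages carry links, so they can drive use of the online materials, which is the exposure in Aim 2b and in the utilization part of Aim 3.
- **Retention.** Regular contact may help to keep families in the study. Section 25.1 plans to compare families lost to follow-up with the overall sample, but does not mention a comparison of losses by arm. One control family lost is 1/25 = 4% of that arm.

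At stake is what a positive six-month result would mean. The plan presents the intervention as targeting error sensitivity and the control as unrelated to it, so readers will credit the content.

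**Working it through.** The plan gives no number of reminders, and no alpha, SD, effect size or power, so there is no figure of its own to reproduce.

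**1. Number of prompts.** Inputs: one reminder a week (section 5.0) and six months between visits (section 4.1).

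6 × (365.25/12) / 7 = 26.1 weeks, so about 26 prompts per reminded recipient. If the messages instead follow the online modules ("24 modules will be offered", section 6.1), the count is about 24. For controls, none is specified.

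**2. Which comparisons are exposed.**

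| Comparison | When measured | Reminders sent by then | Exposed to the active-versus-control gap? |
|---|---|---|---|
| Aim 1, active v control | Pre to post within the baseline visit | 0 | No |
| Aim 2, active v control | Six months | About 26 v none specified | Yes |
| Aim 2a, among active arms | Six months | Controls not involved | No |
| Aim 3, active v control | Six months | About 26 v none specified | Yes |

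**3. Illustration of size.** Assumptions, none of them from the documents: two-sided alpha 0.05, a normal approximation for two means, and reminders that by themselves shift an outcome by d = 0.1, 0.2 or 0.3 SD while the error-sensitivity content does nothing.

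SE with everyone followed: √(1/150 + 1/25) = 0.216 SD.

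SE at 90% retention (section 25.1), applied equally to both groups, giving 135 v 22.5: √(1/135 + 1/22.5) = 0.228 SD.

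P(significant) = Φ(d/SE − 1.96) + Φ(−d/SE − 1.96)

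| Assumed contact-only effect d | 150 v 25 | 135 v 22.5 |
|---|---|---|
| 0 | 5.0% | 5.0% |
| 0.1 | 7.5% | 7.2% |
| 0.2 | 15.2% | 14.2% |
| 0.3 | 28.4% | 26.1% |

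For example, at d = 0.2 with 150 v 25: 0.2/0.216 = 0.926, and Φ(−1.034) + Φ(−2.886) = 0.152.

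**4. After the fix.** With reminders on the same schedule in both groups, the scheduled difference falls from about 26 to 0 per reminded recipient. The sample size does not change.

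**The case against.** The strongest reply is that the plan is silent on control reminders; it does not rule them out. The control is described in a few sentences and is said to have been used before, and its earlier procedures are not in the documents. A reader might infer that controls definitely receive nothing. The text does not say so, and the count of 26 against none holds only if the plan is run as written. That limit stands. It does not remove the point, because the plan assigns reminders by condition and the control description is otherwise specific about format, recipients, topic and online access.

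A reader might also infer that every active-versus-control comparison is confounded. The documents do not support this:

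- Aim 1 is complete before any reminder goes out, and the control paragraph of section 5.0 makes showing initial target engagement the condition for future studies.
- The reminders recall the session's own concepts and link to its materials, so they are part of the intervention. Randomization still gives a valid comparison of that package with control; only attribution to content is limited. Testing a package is a legitimate choice for a study that describes itself as a first step.

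Two further objections stand. The documents contain no evidence on how far reminders move outcomes or dropout, so the percentages above are conditional illustrations; at 0.1 SD the excess over 5% is small. Nor do they give a reason to think that reminders alone would change the six-month ERN, so the concern lies mainly with reported measures and retention. Finally, the plan does not say who is messaged in the child-only arm (50 dyads with children aged 5 to 7), or whether a parent/child family gets one message or two. The count is therefore per reminded recipient and is not established for all 150 active dyads.

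**Conclusion.** The point holds for the six-month active-versus-control comparisons in Aims 2 and 3. Weekly reminders are written for the active conditions and not for the control. If the trial is run that way, an observed difference could not be divided between error-sensitivity content and about 26 weekly prompts. The exposure is greatest for reported error sensitivity and anxiety and for retention. It does not reach Aim 1 or Aim 2a, and it does not invalidate the randomized comparison of the whole package with control.

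The size of any distortion cannot be derived from the documents. Under assumed contact-only effects of 0.1 to 0.3 SD and two-sided alpha of 0.05, the chance of a significant result without any content effect runs from about 7% to 28%, depending on the effect and on retention. The correction is cheap and would improve what the six-month results can show, so it should be made.

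**What to change.** Amend the control paragraph of section 5.0 to state that control families receive weekly reminders by the same channel and at the same frequency as active families, recalling self-care concepts and linking to the self-care materials, with use tracked in the same way.

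In the same section, state who receives the reminders in the child-only arm. In the analysis plan (section 17.1), add that contacts sent and retention will be reported by arm.

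If reminders are deliberately kept to the active arms, say so and limit the six-month conclusion to the whole package of content plus reminders.

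The cost is a few sentences of text and one automated message stream to 25 families, with no change in sample size.
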